#### Treatment safety (pharmacovigilance):

Although we will not have adequate statistical power for a comparative analysis of rare and long-term latent adverse events of the different agents within the confines of this three-year project due to the relatively small patient numbers and short follow-up period, we will still be able to conduct a meaningful descriptive analysis of more common adverse events collected over an at least one-year period for each treatment modality.

The initial analyses will consist of comparisons in baseline status between the individuals in the treatment cohorts. For the purposes of analysis (initially) follow-up time will be censored in both cohorts if there is switching to another class of biologic therapy and censored in the standard therapy group if there is switching to a biologic agent. The adverse events of interest are calculated per person time of follow-up, after the start of therapy.

Sample size of the novel biologics/small molecule exposure group will be largely determined by external factors, including:

- 1) NICE technology assessments and resulting recommendations;
- 2) whether NICE indicates the need for pharmacovigilance and recommends patients are registered in our registry;
- 3) funding of by NHS, and
- 4) uptake by prescribing dermatologists.

The size of the comparison cohort will be more under our control. However, it is difficult to anticipate the magnitude of rate differences for adverse events between the cohorts as patients from all groups are likely to have had prior exposure to immunosuppressive drugs.

Assuming i) the risk of adverse event is proportional to the length of exposure with equal risk per year (note this may not be so), ii) power of 80%, and iii) a significance level of 5%, the following applies:

Annual adverse	Rate ratio	Person years exposure
event rate		per group
1/10,000	2	235,508
1/1000	2	23,590
2/1000	2	11,817
1/100	2	2,321
2/100	2	1,146
4/100	2	551
5/100	2	437
10/100	2	201

For guidance, the estimated risk of certain adverse events are as follows:

Squamous cell carcinoma with ciclosporin use 1 in 320 Non-melanoma skin cancer 1 in 1,000 Melanoma in high dose PUVA (phototherapy) 1 in 1,666 Melanoma in normal person 1 in 10,000

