#### Adverse events/pharmacovigilance:

Drug adverse events are calculated per person time of follow up, after the start of therapy. Time-dependent regression analyses will be undertaken to compare event rates between groups, using standard multivariable analyses to reduce confounding. We will explore the use of other statistical techniques, including propensity score matching, to accommodate confounding by indication. As children and adolescents may have a different phenotype of atopic eczema compared to adults and may respond differently to systemic therapy, we will explore this further in comparative analyses.

Estimating the risk of rare adverse effects with a smaller signal, especially lymphoma will be facilitated by long-term linkage to the national cancer registry (in addition to the control group). The risk window for cancer being defined as once exposed always at risk. Where two biologicals have been used, the proportion of time spent on each will define its possible contribution to risk. Where the adverse event is rare or where a biological intervention is under-represented in the register, the numbers of patient's data can also potentially be increased by sharing data with other compatible registers such as those operating in Germany, Italy, Spain, France, Denmark, and the Netherlands.

The aim in the long-term is to recruit at least 4,000 patients on conventional treatments and also at least 2,000 on each biological intervention (depending on the uptake of these drugs in clinical practice). 4,000 patients in

each cohort, biologicals and conventional treatment would give an exposure of 12,000 patient years in each group. This would give power to detect at least a 3- or 4-fold increase in risk of events occurring at a frequency of 1 in a 1000 or 1 in 2000 patients. Rarer events would be detected if the relative risks were higher.

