#### 10.2 Notes on adverse event inclusions and exclusions

#### **10.2.1** Include

An exacerbation of a pre-existing illness

- An increase in frequency or intensity of a pre-existing episodic event/condition.
- A condition (even though it may have been present prior to the start of the study) detected after study drug administration.
- Continuous persistent disease or symptoms present at baseline that worsens following the administration of the study treatment.
- Laboratory abnormalities that require clinical intervention or further investigation (unless they are associated with an already reported clinical event).
- Abnormalities in physiological testing or physical examination that require further investigation or clinical intervention.
- Injury or accidents.

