#### 10.2.2 Do not include

- Medical or surgical procedures the condition which leads to the procedure is the adverse event.
- Pre-existing disease or conditions present before treatment that do not worsen.
- Situations where an untoward medical occurrence has occurred e.g. cosmetic elective surgery.
- Overdose of medication without signs or symptoms.
- The disease being treated or associated symptoms/signs unless more severe than expected for the patient's condition.

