# 10.7 Reporting procedures

All adverse events should be recorded from initiation of treatment until withdrawn from study. Depending on the nature of the event the reporting procedures below should be followed. Any questions concerning adverse

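### Section 9.4 counts cancers from the start of therapy with no latency allowance, so cancers already present but undiagnosed enter the exposed rate; a lagged analysis should stand beside it

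*Protocol*

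**What the plan says.** Section 9.4 (adverse events/pharmacovigilance) sets the denominator: "Drug adverse events are calculated per person time of follow up, after the start of therapy". For cancer it adds: "The risk window for cancer being defined as once exposed always at risk". No lag, latency period or early-event exclusion is stated. Section 10.7 starts event recording at the same point: "All adverse events should be recorded from initiation of treatment until withdrawn from study".

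Two rules in section 10.2 bear on a disease that predates the drug. Section 10.2.1 lists for inclusion: "A condition (even though it may have been present prior to the start of the study) detected after study drug administration". Section 10.2.2 lists for omission: "Pre-existing disease or conditions present before treatment that do not worsen". Neither says which governs a cancer that was present but not yet diagnosed when treatment began.

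For patients who have had two biologics, section 9.4 shares the risk: "Where two biologicals have been used, the proportion of time spent on each will define its possible contribution to risk". It also plans time-dependent regression to compare event rates, and linkage to the national cancer registry.

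**The concern.** The ever-exposed rule settles when the cancer window closes (never) but lets it open on the first day of treatment. A tumour diagnosed in the first weeks or months will often have been there before the drug. Section 9.3 itself speaks of "rare and long-term latent adverse events", although there it is explaining why the three-year project cannot compare them. Counting such an outcome at full weight from day one sits awkwardly with that description.

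Malignancy risk is named in the secondary safety objective, so the rate ratio matters. Cancers unrelated to exposure that are added to both groups dilute a real effect. If follow-up differs between drugs, these early cases weigh more heavily on the drug with less person-time. The protocol fixes this window itself, so the point is not merely a detail left to an analysis plan.

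**Working it through.** **1. The plan's own figure.** Section 9.3 gives 23,590 person-years per group for a rate ratio of 2 at 1 in 1,000, with 80% power and a 5% level (taken as two-sided). The pooled two-proportion formula is

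n = [1.96·√(2·p̄·(1−p̄)) + 0.8416·√(p₁(1−p₁) + p₂(1−p₂))]² / (p₂−p₁)²

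With p₁ = 0.001, p₂ = 0.002 and p̄ = 0.0015 it gives 23,511, which agrees closely. The other seven rows also reproduce. No stated number is wrong on this point.

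**2. Model for the early cases.** Let λ be the background rate, π the proportion of starters with an undetected cancer that surfaces during follow-up, and F the mean follow-up in years. With no drug effect, the observed rate is λ + π/F.

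- λ = 1 in 1,000 per year is an assumption; section 9.3 lists non-melanoma skin cancer at 1 in 1,000.
- 4,000 patients and 12,000 patient-years per group come from section 9.4, so F = 12,000/4,000 = 3 years.
- π = 0.05% to 0.1% (2 to 4 cases in 4,000) is an assumption; the documents give no figure.

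**3. Equal follow-up, true rate ratio 3.** Expected cancers are 36 versus 12. Adding the same number of early cases to each group:

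- 2 cases: (36+2)/(12+2) = 38/14 = 2.71
- 4 cases: (36+4)/(12+4) = 40/16 = 2.50

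With no drug effect the ratio stays at 14/14 or 16/16 = 1.00.

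**4. Unequal follow-up, no drug effect.** Assume 4,000 starters on each drug, with 1 year on one and 3 years on the other.

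| Undetected at start | 1 year (4,000 PY) | 3 years (12,000 PY) | Ratio |
|---|---|---|---|
| 0.05% | (4+2)/4,000 = 1.50 per 1,000 | (12+2)/12,000 = 1.17 per 1,000 | 1.29 |
| 0.1% | (4+4)/4,000 = 2.00 per 1,000 | (12+4)/12,000 = 1.33 per 1,000 | 1.50 |

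The number of starters cancels from the ratio and affects only precision.

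**5. A second mechanism as a check.** Suppose instead that the detection rate is m times background during the first L years. The average relative rate is [m·L + (F−L)]/F. For L = 1, F = 1 versus 3:

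- m = 1.5: 1.5/1.167 = 1.29
- m = 3: 3/1.667 = 1.80

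For L = 0.5 the range is 1.15 to 1.50. At equal F it is 1.00.

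**6. The two-biologic split.** A cancer found 3 months after moving to a second biologic, following 12, 24 or 36 months on the first, is charged to the second at 3/15 = 20%, 3/27 = 11% or 3/39 = 8%. The older drug carries most of it.

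**7. Cost of a lag.** With 3 years each, a 6-month lag leaves 4,000 × 2.5 = 10,000 person-years, and a 12-month lag 4,000 × 2 = 8,000. Power at a two-sided 5% level, from the same formula solved for power with constant rates over time:

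| Rate ratio, background | 12,000 PY | 10,000 PY | 8,000 PY |
|---|---|---|---|
| 3, 1 in 1,000 | 0.93 | 0.89 | 0.81 |
| 4, 1 in 1,000 | 0.996 | 0.99 | 0.97 |
| 3, 1 in 2,000 | 0.69 | 0.61 | 0.52 |
| 4, 1 in 2,000 | 0.91 | 0.85 | 0.77 |

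In the setting of step 4, if all early cases surface within 6 months, a 6-month lag leaves 2 events in 2,000 person-years against 10 in 10,000, a ratio of 1.00. A 12-month lag leaves nothing for the drug with one year.

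**The case against.** A reader might infer that the adverse event rules charge every pre-treatment condition to the drug. They do not. Section 10.2.2 omits known disease that does not worsen, and section 10.2.1 speaks of presence before the study, not before treatment. These rules also govern recording; causality is judged separately under section 10.4. That part of the objection stands. What remains is that the two lists are not reconciled for an undiagnosed cancer, and that the window in section 9.4 is defined by exposure and time without reference to the causality judgement. Registry linkage can also bring in diagnoses that the site forms did not capture.

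A reader might also infer that the newest drugs suffer most. The documents give no follow-up by drug. That inference needs shorter follow-up and a comparison not aligned on time since start. The planning scenario in section 9.4 has equal exposure in each group, and the two-biologic split pushes early cancers towards the older drug. The split does not cover first-time starters or a move from conventional therapy to a biologic.

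Time-dependent regression could remove much of the between-drug distortion, but only if time since start is modelled, which is not stated. The censoring in section 9.3 ("follow-up time will be censored in both cohorts if there is switching to another class of biologic therapy") concerns when follow-up ends, not when the window opens.

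Finally, the size is modest. The ratios in step 4 rest on 6 versus 14 and 8 versus 16 events. Using √(1/a + 1/b) on the log scale, the 95% intervals are about 0.49 to 3.35 and 0.64 to 3.50. Section 9.4 claims to detect only 3- or 4-fold increases. This is fair, and it limits the weight of the point without removing the dilution.

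**Conclusion.** The point holds in a limited form. As written, section 9.4 admits cancers that were present but undiagnosed at first exposure, at full weight. At equal follow-up this biases a true rate ratio towards 1 (3 becomes 2.71 to 2.50 with two to four early cases per group). With unequal follow-up, and no alignment on time since start, it raises the rate of the drug followed for less time (1.29 to 1.50 for 1 versus 3 years with no effect).

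These sizes rest on the assumed prevalence, background rate and follow-up, none of which the documents supply by drug. The documents do not support a claim that any particular class of drug is disadvantaged.

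**What to change.** In section 9.4:

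- Keep the unlagged ever-exposed cancer rate.
- Add a pre-stated lagged analysis that leaves out both events and person-time before the lag ends, for example 6 and 12 months after first exposure.
- State that the time-dependent regression compares drugs at equal time since first exposure.
- List the cancers diagnosed before the lag ends separately, by drug.

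In section 10.2, reconcile 10.2.1 with 10.2.2 for a cancer present but undiagnosed at the start: still record it, with a flag that it was likely pre-existing.

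The cost is a few sentences, one data field and a little analysis work. The lagged estimate is less precise (step 7), and a drug with only one year of follow-up contributes little or nothing to it at 12 months. The two results should therefore be reported together.

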## **2 PROTOCOL SUMMARY AND STUDY SCHEDULE**

Study title:	The UK-Irish A topic eczema S ystemic T her A py R egister (A-STAR)		
Protocol Short Title/Acronym:	A-STAR		
Sponsor:	King's College London & Guy's & St Thomas' NHS Foundation Trust		
Chief Investigator:	[name]		
IRAS number:	237309		
Study design:	Multicentre, prospective, observational clinical registry of paediatric and adult patients on systemic immuno-modulatory therapies.		
Study participating centres:	Although we will initially start in highly specialised tertiary dermatology departments, all dermatology departments in the UK and Ireland are invited to express an interest to become a study participating centre.		
Population:	Children (no lower age cut off) and adults with atopic eczema (UK Working Party diagnostic criteria), starting on or switching to another systemic immuno-modulatory therapy (e.g. CsA, AZA, MTX or biologic treatments).  The study aims to monitor patients for at least 12 months but if possible for 10 years.		
Study Duration:	A-STAR is a long-term study, with the aim to continue study activities for as long as funding is available.		
Primary Objective:	To establish the short- and long-term effectiveness of systemic immune-modulatory therapies in adults and children.		
Secondary Objectives:	Clinical data collection:  - To assess the short- and long-term safety (pharmacovigilance) of these therapies, for instance with regard to malignancy risk, serious infections and cardiac and CNS abnormalities.  - To establish a collection of health economic data for cost-effectiveness research.		
	A-STAR Bioresource: -To establish a collection of biomaterial for molecular and stratification studies.		
Sample Size:	We aim to extend the register to research active dermatology departments in the UK and Ireland, aiming to recruit at least 4,000 patients on conventional systemic therapy and 2,000 patients on novel biologics/small molecules.		
Study conduct and schedule:	The study is observational and does not involve a study-specific intervention.		

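### The biologic recruitment targets in sections 2 and 9.4 conflict, the rare-event power statement needs two biologics pooled and an unstated three years per patient, and the person-year table is slightly low for common events

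*Protocol*

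**What the plan says.** The biologic target appears in two forms, and the power statement uses a third number.

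- Section 2, Sample Size: "aiming to recruit at least 4,000 patients on conventional systemic therapy and 2,000 patients on novel biologics/small molecules". This is 2,000 for the whole class.
- Section 9.4, Adverse events/pharmacovigilance: "The aim in the long-term is to recruit at least 4,000 patients on conventional treatments and also at least 2,000 on each biological intervention". This is 2,000 per drug, and the text makes it conditional on uptake.
- The next sentence of section 9.4 takes 4,000 in "each cohort, biologicals and conventional treatment would give an exposure of 12,000 patient years in each group". From this it claims enough power for a three- or four-fold rise in risk where the background frequency is 1/1000 or 1/2000. No power level is given and no follow-up per patient is named.

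On follow-up, section 2 (Population) says: "The study aims to monitor patients for at least 12 months but if possible for 10 years". Section 9.3 initially censors follow-up at a switch to another class of biologic, or from standard therapy to a biologic.

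Section 9.3 also tabulates person-years per group for a rate ratio of 2 with 80% power at the 5% level. It assumes that "the risk of adverse event is proportional to the length of exposure with equal risk per year", while noting that this may not be so. Section 9.4 confirms that adverse events are analysed per person-time.

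**The concern.** A reader of section 9.4 is told what size of safety signal the register can detect. That depends on two inputs the reader cannot check: how many biologic patients are in the comparison, and how long each is exposed. The class target in section 2 supplies half the 4,000. The per-drug target in section 9.4 reaches 4,000 only when two drugs are combined. The step from 4,000 patients to 12,000 patient-years is not explained. Safety is a stated secondary objective, so if the real exposure is smaller, the absence of a signal would be given more weight than the data can bear.

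The section 9.3 table raises a smaller question of the same kind. Its column is labelled as exposure time, but the figures for common events look like numbers of people.

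**Working it through.** **1. Implied follow-up.** 12,000 patient-years / 4,000 patients = 3 years per patient. Two biologics at 2,000 each give 4,000 pooled; the section 2 target gives 2,000 × 3 = 6,000 patient-years.

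**2. Power of the section 9.4 statement.** Inputs: background 1/1000 or 1/2000, read as a yearly rate because the statement works in patient-years; risk ratios 3 and 4; two-sided 5% (assumed). Method: exact conditional test. Given the total number of events, the biologic share is binomial with null probability T1/(T1+T0) and alternative RR·T1/(RR·T1+T0). Power is averaged over a Poisson total with mean T0·r + T1·RR·r.

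Example: 12,000 against 12,000 patient-years, 3-fold at 1/2000. Expected events are 12,000/2000 = 6 and 3 × 6 = 18. Exact power is 63% (69% by a normal approximation).

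| Conventional v biologic patient-years | Basis | 3-fold, 1/1000 | 4-fold, 1/2000 | 3-fold, 1/2000 |
|---|---|---|---|---|
| 12,000 v 12,000 | section 9.4 as written | 93% | 90% | 63% |
| 12,000 v 6,000 | section 2 target, 3 years | 80% | 75% | 46% |
| 8,000 v 4,000 | section 2 target, 2 years | 60% | 56% | 31% |
| 4,000 v 2,000 | section 2 target, 1 year (lower bound) | 31% | 26% | 13% |

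The normal approximation is kinder. It gives 83%, 80% and 58% in the second row, and 44%, 43% and 28% in the last. The fourth pair, 4-fold at 1/1000, has above 99% power in the first row and 97% in the second.

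**3. The section 9.3 table.** Two formulas, with r1 = r, r2 = 2r, z = 1.96 and 0.8416:

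- Two proportions: n = [1.96·√(2p̄(1−p̄)) + 0.8416·√(p1(1−p1)+p2(1−p2))]² / (p2−p1)², where p̄ is the mean of p1 and p2.
- Constant rate: PY = (1.96+0.8416)²·(r1+r2)/(r2−r1)² = 7.849 × 3/r = 23.55/r.

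| Rate | Stated | Two proportions | Constant rate | Rate formula v stated | Power of stated PY (score test) |
|---|---|---|---|---|---|
| 1/10,000 | 235,508 | 235,430 | 235,467 | equal | 80% |
| 1/1000 | 23,590 | 23,511 | 23,547 | −0.2% | 80% |
| 2/1000 | 11,817 | 11,737 | 11,774 | −0.4% | 80% |
| 1/100 | 2,321 | 2,319 | 2,355 | +1.5% | 79% |
| 2/100 | 1,146 | 1,141 | 1,178 | +2.8% | 79% |
| 4/100 | 551 | 553 | 589 | +6.9% | 77% |
| 5/100 | 437 | 435 | 471 | +7.8% | 77% |
| 10/100 | 201 | 199 | 236 | +17% | 74% |

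The two-proportion formula reproduces every stated row closely. The two formulas agree for rare events and separate as events become common. By the exact test, 201 person-years per group at 10/100 gives 70% power.

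**The case against.** **Targets.** A reader might infer that the power statement simply assumes twice the biologic patients the plan recruits. The documents do not support that. Section 9.4 aims for 2,000 on each biologic and writes of biologics as one cohort, so two drugs at target make 4,000. The per-drug target and the power statement are compatible; the conflict is with section 2.

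**The claim itself.** The statement pairs two ratios with two frequencies. Read in parallel (3-fold with 1/1000, 4-fold with 1/2000) it has 93% and 90% power on its own 12,000 patient-years. Only the cross-combination, 3-fold at 1/2000, fails, and the text does not clearly assert it. It does not exclude it either.

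**Follow-up.** A reader might infer that the one-year row is what the register will deliver. It is not: 12 months is the minimum, the aim is up to 10 years, and patients are followed even off treatment. For cancer, section 9.4 counts a patient as at risk indefinitely after first exposure, so censoring at a switch matters mainly for other events. This stands, and one year is only a lower bound.

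**The table.** It is not an arithmetic slip, since it reproduces under a standard formula. Its last three rows need at most 589 person-years, which one year on 2,000 patients exceeds, so no conclusion about the long-term register turns on them.

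**Hedging.** Section 9.3 already disclaims power for rare and latent events within the three-year project, and section 9.4 adds cancer-registry linkage and possible pooling with other registers. But the long-term power statement carries no such caution about its own inputs.

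**Conclusion.** The point holds in a limited form. Sections 2 and 9.4 give different biologic targets. The rare-event statement depends on pooling two biologics at target and on a mean of three years per patient, and it states neither. On its own 12,000 patient-years per group it supports 3-fold at 1/1000 and 4-fold at 1/2000, but not 3-fold at 1/2000 (63% exact, about 69% approximate).

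Using the section 2 target costs a moderate amount of power if the three years are kept (80% and 75% for the two supported pairs). Mean exposure is the more sensitive input: at two years each, the same pairs fall to 60% and 56%.

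The table labels a two-proportion result as person-time. Rows at 2/100 and below are within 3% of the rate formula; the last three understate exposure by about 7%, 8% and 17% of the stated figure, for 77%, 77% and 74% power where 80% is claimed.

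These figures assume two-sided 5% testing, constant rates, frequencies read as yearly, and no confounding adjustment.

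**What to change.** 1. Reconcile the biologic target in section 2 with section 9.4: either 2,000 for the class or 2,000 per drug.
2. In section 9.4, say whether the power statement pools biologics or applies to one drug.
3. State the assumed mean years of exposure and give power for it, for example at 1, 2 and 3 years as tabulated above, with one year marked as a lower bound.
4. Limit the claim to 3-fold at 1/1000 and 4-fold at 1/2000, and attach the power level and the patient-years on which it rests.
5. In the section 9.3 table, replace the last three rows with 589, 471 and 236 person-years, and the 1/100 and 2/100 rows with 2,355 and 1,178. State that the test is two-sided, if it is.

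This changes text and one table, with no extra recruitment. The downside is that the stated detection figures become less favourable.
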